## **Secondary objectives:**

# (S1) To demonstrate that worsening of MS-related disability is associated with loss of thalamus volume also if loss of whole brain volume is within the normal range.

Based on the individual results for TVL and BVL derived from three routine MRIs, the study population will be divided into four distinct subgroups as suggested by Opfer et al. (2020) and shown in Figure 4.

**Figure 4.** Clinical characteristics of group 2 ( $\sim$ 25% of all patients) are of particular interest and whether group 2 is statistically distinct with regard to clinical and imaging data.

The probable frequencies for these groups were also taken from this paper:

**Group 1**: normal BVL, normal TVL (estimated frequency ~50% of the total relapsing-remitting MS population); **Group 2**: normal BVL, pathological TVL (~25%); **Group 3**: pathological BVL, pathological TVL (~25%); **Group 4**: normal TVL, pathological BVL (~0%)

We will use the cut-offs for normal and pathological TVL presented in Opfer et al. (2020) and corresponding cut-offs for BVL as published in Opfer et al. (2018a and 2018b).

At month 24 study subjects shall be grouped based on their individual EDSS increase in patients with (confirmed) disability progression and patients without disability progression.

Dichotomization is based on the following cut-offs:

**Group A** (with evidence of disability progression / confirmed disability progression)

- −1.0 increase for study subjects with baseline EDSS scores from 1.0 to 5.0
- −0.5 increase for study subjects with baseline EDSS scores equal or higher than 5.5

**Group B** (no evidence of disability progression)

We will perform a chi-square test to see if there is a significant difference between the frequency of patients with progressive disability (group A) and without evidence of progressive disability (group B).

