#### **Definitions of Study Variables**

| Event                                  | Study variable   | Operational definition   |
|--|------------------|--|
| Documentation
of medical
history | Age              | Age at index date  |
|  | Gender           | trivial  |
|  | Therapy          | Documentation of previous and current treatments and medications related to MS |
|  | Disease duration | Documentation of time since first MS diagnosis                                 |
| Assessment of                          | Relapse activity | Number of relapses within the last 12 months prior to enrollment               |

| inclusion and exclusion       | T2 lesion load                | Number of T2 lesions at time of assessment as defined by MRI   |
|-------------------------------|-------------------------------|--|
| parameters                    | New / enlarging T2
lesions | Number of new or one enlarging T2 lesions within the last 12 months prior to enrollment as defined by MRI  |
|                               | Gd-enhancing lesion           | Number of Gd-enhancing lesions within the last 12 months prior to enrollment as defined by MRI   |
| Assessment of clinical status | Therapy change                | Therapeutic regimen at the time of visit; therapy is subject to change   |
|                               | Relapse activity              | Number and time of relapses since last visit; assessment and documentation whether EDSS worsening is caused by relapses  |
|                               | Diagnosis                     | Documentation of current diagnosis   |
| Assessment of clinical scores | Disability                    | EDSS is used to quantify disability and disability progression over time in MS. Based on a neurological examination, 8 functional systems (visual, brain stem, pyramidal, cerebellar, sensory, bowel & bladder, cerebral, and other functions) are scored from 0 (no disability) to 5 or 6 (more severe disability). Ambulation is assessed based on the distance the patient is able to walk, whether assistance is required or restrictions are present. |
|                               | Disability progression        | Disability progression is defined as 1.0-point increase for patients with a baseline EDSS of 0 to 5.0, and 0.5 points for scores equal or higher than 5.5.   |

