## Outcomes/Endpoint Variables

Primary hypothesis and primary endpoint

The change of MS-related disability during a period of 24 months is inversely associated with the change of thalamus volume during the same period.

MS-related disability will be characterized by the Expanded Disability Status Scale (EDSS). The EDSS will be determined at inclusion (baseline), at 24 months after inclusion, and at additional visits at time intervals approx. every 6 months in between. The annual change of EDSS during the 24-month time period will be computed by linear regression of EDSS versus time including all visits. The change of thalamus volume will be determined in consecutive high-resolution T1w-MRI using a deep-learning based method developed and validated by JDX (Opfer et al. 2020). TVL will be calculated for each pair of two consecutive MRI scans using an advanced and validated method from Opfer et al (2020). The primary endpoint is the Pearson coefficient of the correlation between the annual change of EDSS and the annual change of the thalamus volume.

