#### Secondary hypotheses and secondary endpoints

(S1) Worsening of MS-related disability is associated with loss of thalamus volume also if loss of whole brain volume is within the normal range.

Patients will be dichotomized with respect to the annual EDSS change during 24 months ('stable disability' versus 'progression of disability'), with respect to the annual change of thalamus volume ('stable thalamus volume' versus 'decline of thalamus volume'), and with respect to the annual change of brain parenchymal volume ('stable parenchymal volume' versus 'decline of parenchymal volume'). The parenchymal volume will be determined from the same T1w-MRI as the thalamus volume using a deep-learning based method developed and validated by JDX. The annual change of the parenchymal volume will be computed by linear regression of parenchymal volume versus time. Predefined cutoffs will be used for dichtomization. The association between dichotomized disability change and dichotomized thalamus volume change will be tested in the subgroup of patients with stable parenchymal volume using the chi-square statistic.

(S2) The change of thalamus volume during 24 months is predictive of the change of disability during the following 12 months (months 24-36).

EDSS will be determined at additional visits at 30 and 36 months. The annual change of EDSS between months 24 and 36 will be determined by linear regression of EDSS versus time including 24, 30 and 36 months. The annual change of EDSS between months 24 and 36 will be dichotomized using a predefined cutoff. The association between dichotomized disability change between 24 and 36 months and dichotomized thalamus volume change between baseline and 24 months will be tested using the chi-square statistic.

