# (S2) To demonstrate that the change of thalamus volume during 24 months is predictive of the change of disability during the following 12 months (months 24-36).

We will build a statistical model based on clinical and MRI (estimated from three MRI measurements sampled at baseline (BL), at month 12 and at month 24) parameters to predict disability progression between month 24 and month 36. EDSS will be determined at additional visits at 30 and 36 months. The annual change of EDSS between months 24 and 36 will be determined by linear regression of EDSS versus time including 24, 30 and 36 months. The annual change of EDSS between months 24 and 36 will be dichotomized using the same predefined cutoff as deployed for (S1) (see above). The association between dichotomized disability change between 24 and 36 months and baseline (BL) parameters and TVL between baseline and 24 months will be tested using the chi-square statistic.

The following parameters will be used:

- Clinical scores / characteristics @ BL:
  - Age and sex

\_

<sup>1 Guideline on clinical investigation of medicinal products for the treatment of Multiple Sclerosis from EMA as of 26 March 2015

- disease duration (DD)
- EDSS
- Therapy
- MRI @ BL
  - z-scores of thalamus and whole brain volume
  - T2 lesion load
- MRI @ BL, month 12 and month 24
  - TVL and BVL

The model will be based on multivariate regression or support vector machines. The performance of the model will be characterized using a receiver operating characteristic (ROC) curve. The ROC will be evaluated with respect to accuracy, area under curve (AUC), sensitivity (true positive rate) and specificity (true negative rate). Within each classifier including both clinical and neuroradiological features, permutation importance will be calculated for each feature and for the random variable: only parameters whose importance are higher than the random variable's importance, will be considered as relevant in the classifier.

Baseline volumes for thalamus and whole brain will be estimated using a novel convolutional neural network-based approach, recently submitted for publication (Opfer et al. 2021).

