
#### Sensitivity analysis

A third category for group A "1.5 increase for study subjects with a baseline EDSS score of 0" shall only be used in a sensitivity analysis as performed in the SUNBEAM and RADIANCE trials.

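### The disability-progression rule behind S1 and S2 is stated inconsistently (baseline EDSS 0 in or out; annual slope or month-24 increase), so some patients change group with the section followed

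*Protocol*

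**What the plan says.** Five places in the protocol bear on who counts as progressing.

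- **Section 3, Definitions of Study Variables:** progression is a "1.0-point increase for patients with a baseline EDSS of 0 to 5.0", with 0.5 points from baseline 5.5 upwards.
- **Section 3, Secondary hypotheses and secondary endpoints:** for S1, "Patients will be dichotomized with respect to the annual EDSS change during 24 months". No numerical cut-off is given, only that cut-offs are predefined. The primary-endpoint text just before it defines the annual change as a slope: "The annual change of EDSS during the 24-month time period will be computed by linear regression of EDSS versus time including all visits".
- **Section 4, Secondary objectives (S1):** "At month 24 study subjects shall be grouped based on their individual EDSS increase in patients with (confirmed) disability progression". Group A needs a 1.0-point "increase for study subjects with baseline EDSS scores from 1.0 to 5.0" or a 0.5-point "increase for study subjects with baseline EDSS scores equal or higher than 5.5". Group B is everyone without evidence of progression.
- **Section 4, Secondary objectives (S2):** the EDSS slope over months 24, 30 and 36 is split at the S1 cut-off.
- **Section 4, Sensitivity analysis:** a 1.5-point category for baseline EDSS 0 "shall only be used in a sensitivity analysis as performed in the SUNBEAM and RADIANCE trials".

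**The concern.** These statements cannot all be followed. A patient with baseline EDSS 0 has a 1.0-point threshold in one section, none in another, and a 1.5-point threshold that may not be used in the main analysis. For other patients the variable being split is either a rate per year or a change over 24 months, and one number cannot serve both.

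The rule is the outcome for S1 and S2. The planned S1 rates of 5% and 15% have no fixed meaning until it is settled, and leaving it open would allow the choice to be made after the data are seen. Baseline 0 will probably occur: the scale starts at 0, the eligibility criteria set no minimum EDSS, and the protocol expects mostly early-stage patients.

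**Working it through.** **1. The plan's own S1 figure.** Inputs (Power/Sample Size, Secondary objectives): progression in 5% of group 1 and 15% of group 2, sizes 196 and 98, alpha 0.05 (two-sided assumed), power 0.80. Pooled two-proportion formula:
- pooled rate = (196 × 0.05 + 98 × 0.15)/294 = 0.0833
- SE under the null = √[0.0833 × 0.9167 × (1/196 + 1/98)] = 0.0342
- SE under the alternative = √[0.05 × 0.95/196 + 0.15 × 0.85/98] = 0.0393
- power = Φ[(0.10 − 1.96 × 0.0342)/0.0393] = 0.799

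The required group 1 size by the same formula is 197, against 196 stated. The planned figure reproduces, so the issue is the definition and not the arithmetic.

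**2. Baseline EDSS 0.** Take the path 0, 0, 0, 1, 1 over months 0, 6, 12, 18, 24.

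| Section | Result |
|---|---|
| Definitions of Study Variables | progression |
| S1 analysis | no cut-off applies: unclassified, or group B by default |
| Sensitivity analysis (1.5 points) | not progression |

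**3. Slope or increase in S1.** Visits at t = 0, 0.5, 1, 1.5, 2 years. Slope = Σ(t − 1)y / Σ(t − 1)², with denominator 2.5. For a sustained 1.0-point step:

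| Step first seen | Numerator | Slope per year | Slope × 2 years |
|---|---|---|---|
| Month 6 | 1.0 | 0.4 | 0.8 |
| Month 12 | 1.5 | 0.6 | 1.2 |
| Month 18 | 1.5 | 0.6 | 1.2 |
| Month 24 | 1.0 | 0.4 | 0.8 |

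For baseline 1.0 to 5.0, all four paths are group A by the month-24 increase, and none is if 1.0 is applied to the annual slope. A steady rise would have to reach 2.0 points over 24 months to give 1.0 per year. Multiplying the slope by two years does not remove the conflict, because the group then depends on when the step occurred.

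**4. S2.** With visits at exactly 24, 30 and 36 months, the middle visit has zero weight and the slope equals the month 36 minus month 24 difference. Off schedule they part in both directions. For a true 1.0-point rise, a last visit 0.6 months late gives 0.94–0.97 per year, and one 0.6 months early gives 1.03–1.07. With only months 24 and 30 available, a 0.5-point rise gives 1.0 per year.

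**5. Illustrative effect on S1 power.** The documents give no share for baseline EDSS 0, so 10%, 20% and 30% are assumed. These patients are taken to progress at the planned rates and to be counted as stable. The Overview patient attrition table expects 433 patients at month 24; at the plan's 50% and 25% for groups 1 and 2 that is about 216 and 108.

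| Share at EDSS 0 | Observed rates | Power, 196/98 | Power, 216/108 |
|---|---|---|---|
| 0% | 5.0% / 15.0% | 80% | 83% |
| 10% | 4.5% / 13.5% | 76% | 79% |
| 20% | 4.0% / 12.0% | 71% | 74% |
| 30% | 3.5% / 10.5% | 65% | 69% |

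If these patients are instead left out of the test, power at 196/98 is 76%, 72% and 66%.

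**The case against.** Several stronger readings are tempting, and the text does not support them.

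- *The slope rule misses every sustained 1.0-point step, so group A nearly empties.* From baseline 5.5 the cut-off is 0.5, and a 1.0-point step first seen at month 12 or 18 has slope 0.6 and is counted. The Missing data handling section accepts two EDSS values, and a 1.0-point step seen only over 0 to 12 months gives slope 1.0. The protocol does not say how many patients gain 2 points or more. Moreover, no section states 1.0 per year for S1; that reading combines the endpoint section's variable with the analysis section's number.
- *The protocol places baseline-0 patients in group B.* It gives them no cut-off. Group B by default is one inference, and leaving them unclassified is another.
- *S2 is also incompatible on slope versus increase.* Both S2 texts use the slope, and on schedule it equals the 12-month increase.
- *S1 power is 65%.* That needs a 30% share at EDSS 0, the minimum group sizes, equal progression rates at baseline 0, and planned rates that include such patients. Those rates come from a cited review that is not at hand.

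It can also be said that the 1.0-to-5.0 band is the footnoted one and may be the intended one. That is possible, but the conflict with the study-variable definition remains. Nor can this be left to an SAP: the protocol states the rule itself, and an SAP could not follow every version.

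**Conclusion.** The rule is wrong as written for S1 and S2. Two contradictions are certain from the text: whether baseline EDSS 0 falls under the 1.0-point rule, and whether S1 splits a slope or a month-24 increase. The second changes the group of any patient with baseline 1.0 to 5.0, five on-schedule visits and a sustained 1.0-point step, provided the 1.0 cut-off is applied to the slope. For S2 what stands is narrower: the inherited baseline-0 gap, no statement whether study-entry or month-24 EDSS sets the threshold, and divergence only with off-schedule or missing visits.

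The power losses in the working are conditional illustrations. The primary endpoint, a correlation using the continuous slope, is untouched.

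**What to change.** Before any data are analysed, reconcile the study-variable definition, the secondary-endpoint text, the S1 and S2 analysis text and the sensitivity analysis to one rule.

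- **S1:** dichotomize on EDSS at month 24 minus baseline, not on the slope, with one stated band that includes baseline 0. The 0-to-5.0 band in Definitions of Study Variables would do this; the sponsor should confirm which band was intended. Keep the 1.5-point rule as the sensitivity analysis.
- **S2:** use EDSS at month 36 minus month 24, and name the month-24 EDSS as the reference that sets the threshold.
- **Both:** state whether progression must be confirmed, since the S1 and sample-size texts put that word in brackets without an interval. State how patients without a month-24 or month-36 EDSS are classified.

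No new data are needed and the primary slope analysis stays. The cost is slightly more than wording. No visit is mandatory and two EDSS values are enough to stay in the study, so patients lacking the month-24 or month-36 visit need a stated rule or are lost from the S1 or S2 test.

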# (S2) To demonstrate that the change of thalamus volume during 24 months is predictive of the change of disability during the following 12 months (months 24-36).

We will build a statistical model based on clinical and MRI (estimated from three MRI measurements sampled at baseline (BL), at month 12 and at month 24) parameters to predict disability progression between month 24 and month 36. EDSS will be determined at additional visits at 30 and 36 months. The annual change of EDSS between months 24 and 36 will be determined by linear regression of EDSS versus time including 24, 30 and 36 months. The annual change of EDSS between months 24 and 36 will be dichotomized using the same predefined cutoff as deployed for (S1) (see above). The association between dichotomized disability change between 24 and 36 months and baseline (BL) parameters and TVL between baseline and 24 months will be tested using the chi-square statistic.

The following parameters will be used:

- Clinical scores / characteristics @ BL:
  - Age and sex

\_

<sup>1 Guideline on clinical investigation of medicinal products for the treatment of Multiple Sclerosis from EMA as of 26 March 2015

- disease duration (DD)
- EDSS
- Therapy
- MRI @ BL
  - z-scores of thalamus and whole brain volume
  - T2 lesion load
- MRI @ BL, month 12 and month 24
  - TVL and BVL

The model will be based on multivariate regression or support vector machines. The performance of the model will be characterized using a receiver operating characteristic (ROC) curve. The ROC will be evaluated with respect to accuracy, area under curve (AUC), sensitivity (true positive rate) and specificity (true negative rate). Within each classifier including both clinical and neuroradiological features, permutation importance will be calculated for each feature and for the random variable: only parameters whose importance are higher than the random variable's importance, will be considered as relevant in the classifier.

Baseline volumes for thalamus and whole brain will be estimated using a novel convolutional neural network-based approach, recently submitted for publication (Opfer et al. 2021).

For most regions-of-interest (ROI) in the brain, MRI-based volume estimates (ROIV) are associated with total intracranial volume (TIV) and age. Thus, TIV and age are confounders of no interest (nuisance covariate) for between-subject comparisons. Careful adjustment for TIV and age is required in order to improve the statistical power to detect effects of interest, but also to avoid spurious effects and misinterpretation of actual effects. We will use the residuals method, to regress TIV and age in a large (n = 5,059) independent group of normal control subjects (normal database). The resulting regression model will be used to compute the residuals of ROIV relative to the model in the subjects of interest (not included in the normal database). The residuals quantitatively characterize the extent to which each individual subject's ROIV deviates from that predicted for normal control subjects with the same TIV and age. Residuals will be transformed to z-scores by scaling them to the standard deviation of the residuals in the normal database.

To avoid data redundancy and reduce variance in classifier performances, we will investigate colinearity of clinical and imaging features using a partial correlation analysis. Specifically, a partial correlation between each pair of features controlling for all the remaining features will be done. This analysis will allow us the removal of confounding effects.

T2 lesion (accumulation) will be assessed by a novel convolutional neural network-based approach (Krüger et al. 2021).

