#### Study procedures

• Expanded Disability Status Scale (EDSS) examination

The EDSS is a standardized, widely accepted, numerical scale method used to evaluate disability in people with MS (Kurtzke 1983). The EDSS is evaluated according to signs and symptoms observed during a standard neurological examination. Based on a neurological examination, 8 functional systems (visual, brain stem, pyramidal, cerebellar, sensory, bowel & bladder, cerebral, and other functions) are scored from 0 (no disability) to 5 or 6 (more severe disability). Ambulation is assessed based on distance the patient is able to walk, whether assistance is required, or restrictions are present. The EDSS score ranges from 0 (normal) to 10 (death due to MS) in 0.5 unit increments. A template or an adaptation of this template, which can be found in the appendix, shall be used for documentation. The study will require the same evaluator to perform all EDSS assessments for an individual patient when possible. In addition, EDSS raters will be certified using the Neurostatus Standardized Examination and Assessment (www.neurostatus.net/training) prior to study initiation and examiners will be recertified every two years throughout the conduct of the study.

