#### Missing data handling

Three MRIs will be available per patient. TVL will be calculated for each pair of two consecutive MRI scans. Annualized TVL between the baseline (BL) and last follow-up (FU) scan will be calculated by multiplying the TVL between the two consecutive scans and dividing the resulting

TVL with the time interval between BL and FU scan. If for a patient only two MRIs are available, the TVL can still be computed in the same way. If only one MRI is available, TVL cannot be computed, and the patient will be excluded from the study.

As explained above EDSS scores will be measured approximately every 6 months. The annual change of EDSS during the 24 months' time period will be computed by linear regression of EDSS versus time including all visits (see Fig. 3). This approach still works if EDSS measurements are missing. At least two EDSS measurement are needed otherwise the patient needs to be excluded from the study.

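### The S2 regression slope over months 24, 30 and 36 is simply EDSS at month 36 minus EDSS at month 24: progression is unconfirmed, and annualising a six-month gap would let one 0.5 step meet the 1.0 cutoff

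*Protocol*

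**What the plan says.** Protocol section 4, Secondary objectives (S2), adds EDSS visits for the extension: "EDSS will be determined at additional visits at 30 and 36 months". The annual change over months 24 to 36 is "determined by linear regression of EDSS versus time including 24, 30 and 36 months", and that slope "will be dichotomized using the same predefined cutoff as deployed for (S1) (see above"). Section 3, Secondary hypotheses and secondary endpoints, gives the same construction: "The annual change of EDSS between months 24 and 36 will be dichotomized using a predefined cutoff".

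The S1 cutoff is in absolute points: "1.0 increase for study subjects with baseline EDSS scores from 1.0 to 5.0", and 0.5 from a score of 5.5 upward. S1 labels the group that meets it "with evidence of disability progression / confirmed disability progression", and the Power/Sample Size section puts the word confirmed in brackets. The Definitions of Study Variables table defines progression as a point increase (1.0, or 0.5 from 5.5) and gives no confirmation interval.

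Two further statements matter. On the scale, Study procedures says: "The EDSS score ranges from 0 (normal) to 10 (death due to MS) in 0.5 unit increments". On incomplete series, Missing data handling says: "At least two EDSS measurement are needed otherwise the patient needs to be excluded from the study". That rule follows a sentence about the 24-month slope, and no different rule is stated for S2.

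Power/Sample Size assumes progression of 5% in pooled groups 2 and 3 and approximately zero in group 1 between months 24 and 36, and arrives at 152 per group.

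**The concern.** A regression on three visits suggests that all three readings inform the outcome and that the middle one steadies it. With equal spacing it does neither. The month-30 score is collected for S2 but cannot support or contradict a rise, and no EDSS visit follows month 36 to do so.

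Two things are at stake. First, S2 rests on a comparator rate of essentially zero, so it tolerates very little false progression. Any false progression occurs in both thalamus groups and also enters the event class of the prediction model. Second, the cutoff is in points while the slope is in points per year. The two agree only when the readings span a full year. Over six months the slope doubles the observed difference.

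**Working it through.** **Inputs from the protocol.** Visits at months 24, 30 and 36; cutoff 1.0 point (0.5 from EDSS 5.5); 0.5-point scale; 5% versus about 0%; type I error 0.05, type II error 0.20; 152 per group. **Assumed, because the protocol gives no figure:** the rating error of a single EDSS reading, SD 0.2 to 0.4.

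**1. The protocol's own figure.** Two-sided test of two proportions, pooled variance, no continuity correction:
n = [1.960·√(2·0.025·0.975) + 0.842·√(0.05·0.95)]² / 0.05² = (0.4327 + 0.1834)² / 0.0025 ≈ 151.9, so 152. The stated size reproduces, with power 0.800.

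**2. Slope weights.** Each weight is (t − t̄)/Σ(t − t̄)².
- t = 2.0, 2.5, 3.0 years: deviations −0.5, 0, +0.5; sum of squares 0.5; weights −1, 0, +1. The slope is EDSS36 − EDSS24, with variance 2 times the reading variance.
- Middle visit one month late: −1.046, +0.110, +0.936. A 1.0 rise seen only at month 36 gives 0.936 and misses the cutoff.
- Middle visit one month early: −0.936, −0.110, +1.046. A 1.0 rise present at both later visits gives 1.046 − 0.110 = 0.936 and also misses.
- Two visits six months apart (24 and 30, or 30 and 36): deviations ±0.25; sum of squares 0.125; weights −2, +2. One 0.5 step gives 2 × 0.5 = 1.0 per year.

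**3. Noise-only progression in a stable patient, EDSS36 − EDSS24 ≥ 1.0.** The unrounded model is 1 − Φ(1/(SD·√2)). The grid model is a simulation with normal error rounded to 0.5 steps, true score 2.0.

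| Assumed SD | Unrounded normal | 0.5-step grid |
|---|---|---|
| 0.2 | 0.02% | 1.1% |
| 0.25 | 0.2% | 2.7% |
| 0.3 | 0.9% | 4.8% |
| 0.4 | 3.9% | 10% |

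Spreading true scores over 1.25 to 4.75 changes the grid column little (0.9%, 2.5%, 4.7%, 9.9%). The unrounded model reaches 5% at SD 0.43. With only two visits six months apart, where one 0.5 step is enough, the grid model gives 18% at SD 0.2 and 33% at SD 0.4.

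**4. Effect on S2.** Let a share f of patients without true progression be counted as progressed in both groups. The rates become f and 0.05 + 0.95f.

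| f | Rates compared | Power at 152 per group | n per group for 80% |
|---|---|---|---|
| 0 | 0% v 5% | 80% | 152 |
| 1% | 1% v 5.95% | 66% | 214 |
| 2% | 2% v 6.9% | 54% | 277 |

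The attrition table expects 368 patients at month 36. At f = 1% the requirement is 2 × 214 = 428.

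**5. Would confirmation at month 30 be a better outcome?** Requiring the 1.0 rise at both months 30 and 36 lowers the grid-model noise rate to 0.1%, 0.5%, 1.2% and 3.4% at the four SDs. It also misses every progression that starts after month 30. If onset is uniform over the year (an assumption), that is half of true events. Power at 152 per group then falls from 80% to 50% without noise. For a true jump of 1.0 it falls from about 53% to 30–35% at SD 0.2, and from about 22% to 14–16% at SD 0.3; the ranges reflect separate simulations.

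**6. Broken-stick slope.** With visits every six months from 0 to 36 and a knot at month 24, the post-24 slope has variance 1.57 times the reading variance, against 2.0. Month 30 receives weight 0.14 and month 36 receives 0.93.

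**The case against.** The strongest reply is that nothing is misclassified. The protocol's definition of progression is a point increase with no confirmation interval. Over 12 months, EDSS36 − EDSS24 is exactly that increase, so the regression is merely redundant. This stands for patients seen at months 24 and 36. A reader might infer from the bracketed word confirmed that S2 breaks a confirmation rule, but S1 offers evidence of progression and confirmed progression as alternatives and states no interval, so there is no rule to break.

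A reader might also infer that rating noise will produce progression at about the 5% that S2 is meant to detect. The protocol does not support this. It gives no rating error, and it provides for rater certification, recertification every two years and the same evaluator when possible. A rate near 5% needs a reading SD of about 0.3 on the grid, which implies that some 40% of readings in stable patients are at least one step off, or an SD of 0.43 in the unrounded model. The claim is therefore conditional. The loss of power at 1% to 2% false progression depends much less on the noise model.

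The two-reading rule is written for the 24-month slope, and handling of a missed extension visit may be settled in an analysis plan that is not shown. That is fair, so the six-month result is stated as conditional.

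Finally, visits are only approximately six-monthly, so the zero weight is nominal. This does not help: the weight that month 30 then receives is set by the calendar, and its sign depends on whether the visit was early or late.

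**Conclusion.** The concern holds in a limited form. At the nominal schedule S2 progression is an unconfirmed difference between two readings, and month 30 carries no weight (about 0.1 if that visit is one month late). This is exact and needs no outside figure.

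The size of the noise problem rests on an assumed reading SD: about 1% to 10% false progressors for SD 0.2 to 0.4 on the grid, and less without rounding. The design is sensitive because it assumes a comparator rate near zero; false progression of 1% or 2% in both groups brings power to about 66% or 54%.

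The clearest defect is conditional on carrying the two-reading rule to S2. A single 0.5 step over six months would then meet a 1.0 cutoff, contrary to the 1.0-point increase in the protocol's own definition, with noise-only rates of 18% to 33%.

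The 152 per group is arithmetically correct, and S2 belongs to an optional extension. The analysis does not show that a rule requiring the rise at both months 30 and 36 should become the S2 outcome: that rule lost power at every noise level tested.

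**What to change.** In section 3 (Secondary hypotheses and secondary endpoints), section 4 (Secondary objectives, S2) and Missing data handling:

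- Define S2 progression as the absolute EDSS increase from month 24 to month 36, set against the stated cutoff, in place of the three-point slope.
- Require both the month-24 and the month-36 value for S2, and do not annualise a six-month difference.
- State plainly that S2 progression is unconfirmed.
- Report two sensitivity analyses, not replacement outcomes: (a) the rise present at both months 30 and 36, noting that it misses progression that starts after month 30; (b) a broken-stick slope over months 0 to 36 with a knot at month 24, noting that it assumes a linear course before month 24.

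The cost is wording only, since all these EDSS values are already planned. The small downside is that patients missing either visit are not classified for S2. The change removes the six-month inflation and the dependence on visit timing. It does not remove rating noise from the month-24 and month-36 readings, so the power loss shown for a non-zero comparator rate remains and should be acknowledged.
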